#### 15.2.2.5 Section 6.2 Exclusion criteria

This section was modified based on amendment changes 3 and 7.

*Old text:*

[...]

7. Planned dual antiplatelet therapy (DAPT) use for the qualifying revascularization procedure of clopidogrel in addition to ASA for ~~>30 days\*~~ after the qualifying revascularization procedure (~~or >60 days for a labeled indication [e.g. drug coated stent or balloon]~~)

*(\*Planned use of clopidogrel not exceeding 60 days for a labeled indication for a device [e.g., stent or balloon] may be allowed; see section 8.1 for further guidance on clopidogrel)*

8. Planned\* DAPT use for any other indication(s) with any P2Y12 antagonists (e.g. percutaneous coronary interventions) in addition to ASA after the qualifying revascularization procedure

*(\*This exclusion criterion refers to the clinical condition at the time of randomization. The use of DAPT with ASA plus P2Y12 antagonists of any type for new indication(s) occurring after randomization is permitted; see Section 7.4.4);*

[..]

11. Systemic treatment with strong inhibitors of both Cytochrome P450 isoenzyme 3A4 (CYP3A4) and p-glycoprotein (P-gp) inhibitors (e.g., systemic azole antimycotics, such as ketoconazole [fluconazole is permitted], and human immunodeficiency virus [HIV]-protease inhibitors, such as ritonavir), or strong inducers of CYP3A4 (e.g., rifampicin, rifabutin, phenobarbital, phenytoin and carbamazepine) ~~at the time of screening or their anticipated use~~ during the study.

- Exclusion criteria related to bleeding risks or systemic conditions:

[...]

14. ~~Medical history of chronic renal failure, any condition requiring dialysis or renal replacement therapy or a renal impairment at screening assessed with an estimated glomerular filtration rate <15 mL/min/1.73 m^2\*~~

*(\*if a patient's eGFR is <30 mL/min/1.73 m^2 prior to the procedure, it must remain to be >15 mL/min/1.73 m^2 72 hours after the procedure to enroll and randomize the patient);*

*New text:*

[...]

7. Planned dual antiplatelet therapy (DAPT) use for the qualifying revascularization procedure of clopidogrel in addition to ASA for ~~>6 months~~ after the qualifying revascularization procedure; it is strongly recommended that any course of clopidogrel is kept to the minimum necessary in accordance with local standard of care and international practice guidelines (typically 30 days, or up to 60 days for some drug-coated products or devices) and is only allowed for up to 6 months for complex procedures or devices in the investigator's opinion that require longer use; see section 8.1 for further guidance on clopidogrel.
8. Planned\* use of any additional antiplatelet agent other than clopidogrel and ASA after the qualifying revascularization procedure

*(\*This exclusion criterion refers to the clinical condition at the time of randomization. The use of DAPT with ASA plus clopidogrel, for new indication(s) occurring after randomization is permitted)*

[...]

11. Systemic treatment with strong inhibitors of both Cytochrome P450 isoenzyme 3A4 (CYP3A4) and p-glycoprotein (P-gp) inhibitors (e.g., systemic azole antimycotics, such as ketoconazole [fluconazole is permitted], and human immunodeficiency virus [HIV]-protease inhibitors, such as ritonavir), or strong inducers of CYP3A4 (e.g., rifampicin,

rifabutin, phenobarbital, phenytoin and carbamazepine) anticipated after randomization or during the study.

- Exclusion criteria related to bleeding risks or systemic conditions:

[...]

14. Any condition requiring dialysis or renal replacement therapy, or a renal impairment at screening assessed with an estimated glomerular filtration rate <15 mL/min/1.73 m^2\*  
*(\*if a patient's eGFR is <30 mL/min/1.73 m^2 prior to the procedure, it must remain to be >15 mL/min/1.73 m^2 72 hours after the procedure to enroll and randomize the patient);*

#### **15.2.2.6 Section 7.3 Treatment assignment**

This section was modified based on amendment change 7.

*New text:*

[...]

The clopidogrel use defining the randomization strata refers to actual clopidogrel use, at randomization, as adjunct treatment for the qualifying revascularization. Specific procedures for treatment assignment through the IxRS will be described in the IxRS manual.

#### **15.2.2.7 Section 8.1 Prior and concomitant therapy**

This section was modified based on amendment change 3.

*Old text:*

[...]

If deemed required by the investigator, the use of clopidogrel ~~for a planned duration of up to 30 days following the qualifying revascularization procedure, or planned duration of up to 60 days in the case of a labeled indication for a device (e.g. drug-coated stent or balloon), is allowed. Justification will need to be documented during the course of this planned use of clopidogrel if the investigator determines that a medical need arises that warrants that clopidogrel be administered for >30 days following the qualifying revascularization, or >60 days in the case of a device.~~ Clopidogrel will not be supplied as a study medication.

[...]

*New text:*

[...]

If deemed required by the investigator, the use of clopidogrel concomitantly with study drugs is allowed at the time of randomization. It is strongly recommended that any course of clopidogrel is kept to the minimum necessary to comply with local standard of care and international practice guidelines (typically 30 days, or up to 60 days for some drug-coated products or devices). Clopidogrel will not be supplied as a study medication.

[...]

### 15.2.2.8 Section 9.1 Tabular schedule of evaluations

This section was modified based on amendment changes 5 and 7.

*New text:*

**Table 9-1: Schedule of assessments - amended**

Timelines	ScV a	Qualifying revascular -ization (Rev)	RxV a (T0)	Treatment Phase						PS-FU 1 Mo post EOT	
				V1	V2	V3	V4	V5-Vx	EOT visit b		
				1 Mo	3 Mo	6 Mo	12 Mo	every 6 Mo			
Visit Window (weeks if not otherwise specified)	-30 days before, to +10 days after, Rev		Up to +10 days after Rev	±10 days	±4	±4	±4	±4		±1	
Type of Visit	Visit		Visit	Visit	Visit	Visit	Visit	Visit	Visit	📞	
[...]											
ABI/TBI h	• g			•	•	•	•	•	•		
[...]											
[...]											

f: Only AE/ SAEs not exempted from adverse event reporting and specified in the protocol need to be documented (see Section 9.6.1.3 (change no.17).  
 g: ABI/TBI values used at screening may be historical (captured in the patient's medical history), but must not be older than 12 months prior to the qualifying revascularization procedure (change no. 5). If an ABI/TBI is performed during screening to assess eligibility, it must be completed prior to, or at the time of the qualifying revascularization (change no. 6).  
 h: ABI/TBI assessments performed after informed consent is obtained must be performed per the guidance in the ABI/TBI Site Manual.

### **15.2.2.9 Section 9.2.1.1 Screening Visit (ScV): 30 days before, or up to 10 days after qualifying revascularization procedure**

This section was modified based on amendment change 5.

*New text:*

- [...]
- perform ABI (or TBI) if no ABI/TBI data are available for the patient within the last 12 months prior to the qualifying revascularization; ABI/TBI assessments performed after informed consent is obtained must be performed per the guidance in the ABI/TBI Site Manual.

### **15.2.2.10 Section 9.3.3 Definition of qualifying revascularization procedure**

This section was modified based on amendment changes 4 and 6.

*Old text:*

For the purposes of the current study, the qualifying revascularization procedure (surgical or endovascular) must be a technically successful procedure in the past 10 days, and hemostasis must be assured.

[...]

**Surgical procedure:** surgical bypass procedures in the lower extremity for PAD ~~distal to the external iliac artery~~. This can include a variety of bypass conduit materials and extra-anatomic operations.

**Endovascular procedure:** catheter-based procedures ~~distal to the external iliac artery~~ and hybrid procedures (those procedures involving aspects of both endovascular and surgical revascularizations).

[...]

*New text:*

For the purposes of the current study, the qualifying revascularization procedure (surgical or endovascular) must include a technically successful procedure distal to the external iliac artery in the past 10 days, and hemostasis must be assured.

[...]

**Surgical procedure:** open surgical procedures in the lower extremity for PAD. This can include a variety of procedures, bypass conduit materials, and extra-anatomic operations.

**Endovascular procedure:** catheter-based procedures and hybrid procedures (those procedures involving aspects of both endovascular and surgical revascularizations) for PAD.

[...]

Sites may be required to submit source documents from the qualifying revascularization procedure for central data verification.

### **15.2.2.11 Section 9.4.1 Assessments and procedures at occurrence of primary efficacy events**

This section was modified based on amendment change 7.

*New text:*

The analysis of study efficacy outcome events will be based on events as adjudicated by the ICAC. Thus, the occurrence of study efficacy outcome events must be reported on Outcome/CV Event reporting forms, as described in the Endpoint Event Site Manual, and will undergo adjudication by the ICAC. All potential coronary ischemic events, cerebrovascular events and peripheral ischemic events should also be reported on the Outcome/CV Event reporting forms.

### **15.2.2.12 Section 9.4.3.2 Secondary efficacy variables**

This section was modified based on amendment change 2.

*New text (incl. changed sequence of bullet points):*

The secondary efficacy variables of the study are:

- time from randomization to the first occurrence of MI, ischemic stroke, coronary heart disease mortality, ALI, and major amputation of a vascular etiology;
- time from randomization to the first occurrence of an unplanned index limb revascularization for recurrent limb ischemia (subsequent index leg revascularization that was not planned or considered as part of the initial treatment plan at the time of randomization);
- time from randomization to the first occurrence of hospitalization for a coronary or peripheral cause (either lower limb) of a thrombotic nature;

- time from randomization to the first occurrence of MI, ischemic stroke, all-cause mortality, ALI, and major amputation of a vascular etiology;
- time from randomization to the first occurrence of MI, all-cause stroke, CV death, ALI, and major amputation of a vascular etiology;
- time from randomization to the first occurrence of all-cause mortality.
- time from randomization to the first occurrence of venous thromboembolic (VTE) events.

#### **15.2.2.13 Section 9.6.1.3.3 Reporting of serious adverse events and study-specific exemptions**

This section was modified based on amendment change 7.

*Old text:*

[...]

2. **Safety outcome events** (i.e., bleeding events occurring after ~~randomization~~) will not be recorded on the AE page and not be reported as SAEs to Sponsor's PV department, but they will be collected on the specific eCRF pages as a safety outcome event.

[...]

*New text:*

[...]

2. **Safety outcome events** (i.e., bleeding events occurring after signing of the ICF) will not be recorded on the AE page and not be reported as SAEs to Sponsor's PV department, but they will be collected on the specific eCRF pages as a safety outcome event.

[...]

ISTH	International Society on Thrombosis and Haemostasis
ITT	Intention-to-treat
IxRS	Interactive web/voice response system
KM	Kaplan Meier
LCEAD	Last Clinical Event Ascertainment Date
LDL	Low-density lipoprotein
MACE	Major adverse cardiac events
MALE	Major adverse limb events
MedDRA	Medical Dictionary for Regulatory Activities
MI	Myocardial infarction
NYHA	New York Heart Association
od	Once daily
p	p-value
PAD	Peripheral Artery Disease
PT	Preferred Term
RRR	Relative risk reduction
SAE	Serious adverse event
SAF	Safety analysis set
SAP	Statistical analysis plan
SOC	System Organ Class
TBI	Toe Brachial Index
TE	Treatment Emergent
TEAE	Treatment Emergent Adverse Events
TIMI	Thrombolysis in Myocardial Infarction

Statistical Analysis Plan

Protocol No.: **BAY 59-7939 / 17454**

Page: 5 of 36

TLF Tables, listings, and figures
USA United States of America
vs. versus
VTE Venous thromboembolism
WIQ Walking Impairment Questionnaire

Statistical Analysis Plan

Protocol No.: **BAY 59-7939 / 17454**

Page: 6 of 36

1. Introduction

Peripheral artery disease (PAD) refers to the atherosclerotic obstruction of the major arteries supplying the lower extremities, sometimes also referred to as lower extremity artery disease. Atherosclerosis of the peripheral circulation, with underlying atheroma and chronic inflammation, leads to progressive occlusion of medium and large arteries, with additional risks of embolism or thrombus formation. Abrupt occlusions and plaque rupture may lead to acute complications such as acute limb ischemia (ALI), similar to an acute coronary syndrome event in the coronary circulation (Becker et al. 2011).

The hypothesis of the VOYAGER study is that rivaroxaban added to standard of care therapy of low-dose acetylsalicylic acid (ASA), has the potential to reduce the incidence of the major cardiovascular (CV) outcomes (i.e., CV death, myocardial infarction (MI), and ischemic stroke) as well as major lower limb vascular events (i.e. ALI and major amputation) in symptomatic PAD patients requiring lower extremity revascularization procedures.

This core statistical analysis plan (SAP) is based on the Global Integrated Clinical Study Protocol BAY 59-7939/17454 version 3.0 and contains definitions of analysis sets, key derived variables and statistical methods for analysis of efficacy and safety for the VOYAGER study. It provides a technical and detailed elaboration of the principal features of the planned analyses, e.g., censoring schemes for time-to-event variables. Amendments and/or appendices to this core SAP may be used to add additional analysis and provide more details on the coding guidelines, data-handling, and output tables and figures.

Titles, mock-ups, and programming instructions for all statistical output (tables, figures, and listings (TLF)) are provided in a separate TLF specifications document.

2. Study Objectives

The primary efficacy objective is:

- To evaluate whether rivaroxaban added to ASA is superior to ASA alone in reducing the risk of major thrombotic vascular events (defined as MI, ischemic stroke, CV death, ALI, and major amputation of a vascular etiology) in symptomatic PAD patients undergoing lower extremity revascularization procedure.

The secondary efficacy objectives are:

- To evaluate whether rivaroxaban added to ASA is superior to ASA alone in reducing the risk of MI, ischemic stroke, coronary heart disease mortality, ALI, and major amputation of a vascular etiology
- To evaluate whether rivaroxaban added to ASA is superior to ASA alone in reducing the risk of an unplanned index limb revascularization for recurrent limb ischemia (subsequent index leg revascularizations that were not planned or considered as part of the initial treatment plan at the time of randomization)

Statistical Analysis Plan

Protocol No.: **BAY 59-7939 / 17454**

Page: 7 of 36

- To evaluate whether rivaroxaban added to ASA is superior to ASA alone in reducing the risk of vascular hospitalizations for a coronary or peripheral event (either limb) of a thrombotic nature
- To evaluate whether rivaroxaban added to ASA is superior to ASA alone in reducing the risk of MI, ischemic stroke, all-cause mortality, ALI, and major amputation of a vascular etiology
- To evaluate whether rivaroxaban added to ASA is superior to ASA alone in reducing the risk of MI, all-cause stroke, CV death, ALI, and major amputation of a vascular etiology
- To evaluate whether rivaroxaban added to ASA is superior to ASA alone in reducing the risk of all-cause mortality
- To evaluate whether rivaroxaban added to ASA is superior to ASA alone in reducing the risk of venous thromboembolic (VTE) events.

The primary safety objective of the study is:

- To evaluate the overall safety and tolerability of rivaroxaban added to ASA compared to ASA alone.

3. Study Design

This study is an international multicenter, randomized, placebo-controlled, double-blind, event-driven phase 3 study.

Following provision of informed consent, subjects who fulfill all inclusion criteria and meet none of the exclusion criteria will be treated with ASA 100 mg once daily (od) and randomly allocated by an interactive voice/web response system (IxRS) in a ratio of 1:1 to additional treatment with either rivaroxaban 2.5 mg or placebo twice daily (bid). The randomization will be stratified by type of procedure and use of clopidogrel (i.e., (i) surgical vs. (ii) endovascular with clopidogrel vs. (iii) endovascular without clopidogrel). Treatments will be balanced within a country for each stratum by block randomization. Randomization and study treatment should commence as soon as possible but no later than 10 days after a successful qualifying revascularization procedure and once hemostasis has been assured. All randomized subjects will receive study medication (either rivaroxaban or placebo) and study ASA in a sufficient quantity until the next scheduled on-site visit and detailed instructions for its administration.

The study is event-driven, and thus, all subjects will be treated (or followed-up in the case of permanent discontinuation of study medication) until the end of treatment (EOT) visit. It is estimated that approximately 6,500 subjects (3,250 per treatment group) are needed to be enrolled in order to have 1,015 subjects experiencing a confirmed primary efficacy outcome event. Due to the event-driven study design, no firm treatment duration can be stipulated for an individual subject. The estimated maximum treatment period for an individual subject is approximately 42 months, and the mean treatment duration is expected to be approximately 30 months. However, this duration may vary depending on the recruitment rate as well as the primary event rate.

Statistical Analysis Plan

Protocol No.: **BAY 59-7939 / 17454**

[figure not shown]
Page: 8 of 36

Subjects who have discontinued study drug treatment prematurely should continue to be followed according to the regular visit schedule, and study efficacy outcome events, bleeding events and vital status must be assessed in these subjects until the end of the study via either clinic visits or telephone contacts.

Throughout the study and at all on-site visits, subjects will be assessed for the occurrence of study efficacy outcome events and bleeding events. Suspected clinical study outcomes (study efficacy outcome and bleeding events) will be assessed independently by an Independent Clinical Adjudication Committee (ICAC) blinded to treatment allocation, and the adjudicated results will be the basis for the final study analyses.

There will be one formal interim analysis, which will occur when approximately 67% of the planned primary efficacy outcomes have accrued and adjudicated.

A simplified schematic of the study design is provided in the following figure:

4. General Statistical Considerations

4.1 General Principles

All variables will be summarized using descriptive statistical methods. The number of patients with data available and missing, mean, standard deviation, minimum, quartiles, median, and maximum will be provided for continuous variables, as appropriate. Frequency tables will be provided for categorical variables. The decision rules will be based on one-sided superiority testing unless otherwise specified, but in addition to the one-sided p-values from the logrank test, two-sided p-values will be reported according to general conventions. The statistical evaluation will be performed by using the software package SAS release 9.2 or higher (SAS Institute Inc., Cary, NC, USA).

4.2 Handling of Non-compliance to Study Treatment or Follow up

A randomized subject who permanently discontinues rivaroxaban or rivaroxaban placebo before their planned EOT Visit for any reason is defined as having had a permanent discontinuation of study medication (including subjects who were randomized but never

Statistical Analysis Plan

started taking any study medication). The reason for permanent discontinuation of study medication will be collected and summarized.

A subject will be considered as lost to follow-up for analysis purposes if contact is not obtained with the subject despite all possible efforts by the site, and the subject's vital status is not obtained and documented in the database at the end of the study.

4.3 Handling of Missing Data

All missing or partial data will be presented in the subject data listing as they are recorded on the case report form (CRF) including best estimate dates of site investigators collected in the clinical database.

Missing or incomplete post-randomization event dates

All efforts will be made to collect complete data for all subjects randomized in this study including visits by telephone contact. Subjects will be followed to the study end and all required data will be collected, regardless of their compliance with study medications or visits.

When an event date is not complete, the date will be estimated according to the following rules but not earlier than randomization date,

- If only the onset day is missing, but the month and year are available:
 - If the month and year are the same as the efficacy cut-off date (ECOD), impute the date as mean of the first day of the onset month/year and the ECOD (rounded up).
 - Otherwise if the month and year are the same as the last contact date alive (see [Appendix A](#)), impute the date as mean of the first day of the onset month/year and the last contact date alive (rounded up). For death event, the last contact alive date +1 day will be used as the death date.
 - Otherwise impute the event date as maximum of the date of randomization + 1 and day 15 of the onset month and year.
- If the onset day and month is missing, but the year available:
 - The minimum possible date is maximum of randomization date + 1 days and January 1st of the onset year.
 - The maximum possible date is the minimum of the ECOD and last contact date alive and December 31th of the onset year.
 - Impute the event date as mean of the minimum possible date and the maximum possible date (rounded up).
 - For subjects who experienced death in the same year as last contact alive date, the last contact alive date +1 day will be used as the death date.
- If the onset date is complete missing, the onset date will be imputed with the randomization date + 1 days.
- For subjects who experienced death during the study and the death date is completely missing, the last contact alive date + 1 day will be used to impute death date. If the last contact alive date is missing, the death date will be imputed as ECOD.

Statistical Analysis Plan

Protocol No.: **BAY 59-7939 / 17454**

Page: 10 of 36

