### 10.3.3.5 Handling of missing data

All efforts will be made to collect complete data for all patients randomized in this study including visits by telephone contact. Patients will be followed to the study end and all required data will be collected, regardless of their compliance with study medications or visits.

When an event date is not complete, the date will be estimated to be the middle date within the period that the event is known to have occurred, e.g., if the event is known to have occurred in the first week of a month, then the date in the middle of that week will be used; if no information is known then the date in the middle of the plausible time period will be used, based on the last contact with the patient prior to the event and the date of contact when information about the event was known.

If a patient experiences a fatal event that is not part of a specific endpoint under analysis, the patient will be considered as having been censored at the earlier date of efficacy cut-off or the time of death. If a patient is lost to follow-up or has withdrawn consent and has not experienced any endpoint events under analysis, the patient will be counted as censored at the last contact date prior to the date of efficacy cut-off, with complete information of the endpoint being analyzed (e.g., for analysis of the primary endpoint, information regarding all components of the primary endpoint need to be available at the contact date).

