4.5 Data Rules

4.5.1 Analysis Dates

For the study, the following date and time window are of relevance for the analysis:

- Efficacy cut-off date:
The trial is designed to be terminated when 1015 patients have experienced a confirmed primary efficacy outcome event. The ECOD is a predicted common date when at least 1015 primary efficacy outcomes are expected to have occurred. It is the last calendar date acceptable for counting events for the primary analysis.
- Trial close-out window:
The time period when all subjects return to the clinic for an EOT visit. All randomized subjects should return for their EOT visit after the ECOD.

For each subject, the following individual dates are of relevance for analysis:

- Randomization date:
The date of randomization as recorded in the IxRS system.
- EOT Visit date:
The date of the EOT visit. If subjects do not have an EOT visit, the date will be missing.
- Date of last contact:
The date of the last documented contact with the subject or a third party (including data on subject survival status, see [Appendix A](#) for details).
- Date of first dose of study treatment:
The date of the first dose of rivaroxaban or rivaroxaban placebo, defined as:
 - Date of first dose from the appropriate CRF page capturing the study medication (rivaroxaban or rivaroxaban placebo) if this date is complete.
 - Date of the earliest logically possible dose of study medication (rivaroxaban or rivaroxaban placebo) administration in cases where the date of first dose is missing or incomplete. See [Appendix D](#) for details of the imputation rules.
- Date of last dose of study treatment:

Statistical Analysis Plan

Protocol No.: **BAY 59-7939 / 17454**

Page: 11 of 36

The date of the last dose of rivaroxaban or rivaroxaban placebo, defined as:

- Date of last dose from the appropriate CRF page capturing the study medication (rivaroxaban or rivaroxaban placebo) if this date is complete.
- Date of the latest logically possible dose of study medication (rivaroxaban or rivaroxaban placebo) administration in cases where the date of last dose is missing or incomplete. See [Appendix D](#) for details of the imputation rules.

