Appendix A: Study Closeout Procedure and Variables used for Censoring

Note: The dates and timeline shown are for illustration purpose only. ECOD= Efficacy cut-off date, EOT Visit=end of treatment visit, PS-FU Visit=Post-study treatment follow-up visit (phone call), DBL=database lock

The executive committee will monitor the accrual of the number of primary events, and when appropriate predict and define an ECOD at which time the pre-defined target number of events for the primary composite endpoint are expected to have occurred. All randomized patients should return for their End of Treatment (EOT) visit after the ECOD.

Events that occur after the ECOD will also be collected and adjudicated. These events will be included in sensitivity analyses but not the primary analysis.

For the implementation of the censoring rules below variables are defined to distinguish between a patient's last contact with information relating to clinical events versus CV-death / all-cause mortality.

- Date of objection to further data collection

This date will be given only for those subjects who expressed objection to further data collection after withdrawal of informed consent.

- Last clinical event ascertainment date

The latest date from regular or unscheduled post-randomization visits or contacts with assessment of clinical events or latest adjudicated clinical event start date.

- Date of last contact alive

The date of the last documented contact with the subject or a third party (including data on subject survival status) derived from the maximum (last clinical event ascertainment date, SAEs date, vital status date, consent withdrawn date or date of objection to further data collection). The resulting maximum date is capped by the death date if the patient died or by the date of clean database. In addition, the date of last contact alive will be the day before the death date, if available, for subjects who die.

Statistical Analysis Plan

Protocol No.: **BAY 59-7939 / 17454**

Page: 33 of 36

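### SAP 4.3 always counts a day-missing event in the cut-off month in the primary analysis, and can date a year-only death to the year before it occurred

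*SAP*

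**What the plan says.** SAP 4.3 treats partial post-randomization event dates in a fixed order.

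**Day missing.** The first branch opens with "If the month and year are the same as the efficacy cut-off date (ECOD), impute the date as mean of the first day"; the other point in that mean is the ECOD, and the result is rounded up. Only if that branch does not apply does the next one use the month of last contact alive. The exception that dates a death to the day after last contact alive sits in that second branch. All remaining cases follow "Otherwise impute the event date as maximum of the date of randomization + 1 and day 15 of the onset month and year".

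**Day and month missing.** The lower bound is the later of two dates: the day after randomization, and 1 January of the year in which the event began. For the upper bound the rule is: "The maximum possible date is the minimum of the ECOD and last contact date alive and December 31th of the onset year". The imputed date is the midpoint between these bounds, again rounded up. There is one exception: "For subjects who experienced death in the same year as last contact alive date, the last contact alive date +1 day will be used".

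Three other places bear on this:
- SAP 4.5.1, on the ECOD: "It is the last calendar date acceptable for counting events for the primary analysis". The same section puts EOT visits after the ECOD.
- SAP Appendix A: "Events that occur after the ECOD will also be collected and adjudicated". It assigns those events to sensitivity analyses only.
- Protocol 10.3.3.5: when an event date is incomplete, "the date will be estimated to be the middle date within the period that the event is known to have occurred". If nothing more is known, the plausible period is based on the last contact before the event and the contact at which the event became known.

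**The concern.** The ECOD decides whether an event belongs to the primary data scope. Under the first branch, an event in the ECOD month with the day unknown is placed inside by construction. A day-missing event in a later month is normally given day 15 of that month and excluded, so inclusion is not a general convention of the SAP.

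Because the ECOD-month branch is tested first, it also overrides the last-contact rule and its death exception. A death can then be dated before a visit at which the patient was alive, and a non-fatal event can be dated after the patient died.

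In the year-only rule, last contact alive serves as an upper bound. For a death it is naturally a lower bound, and Protocol 10.3.3.5 uses the last contact before the event in that way. A long gap between last contact and death is realistic: Protocol 6.3.1 has vital status obtained at study end for patients who withdrew consent, and allows registry searches for patients who were lost. Under Protocol 9.4.2 a death is taken as CV unless a non-CV cause is clearly shown, so a misdated death can be a primary event.

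**Working it through.** The documents give neither a calendar ECOD nor a count of partial dates. All example dates below are assumptions.

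**1. Day missing, ECOD month.** If the ECOD is day d, the imputed day is (1 + d)/2, rounded up.
- d = 1 gives 1 and d = 2 gives 2, the ECOD itself.
- d = 8 gives 5; d = 15 gives 8; d = 25 gives 13; d = 30 gives 16.
- From d = 3 onward the date is strictly before the ECOD. It is never after it in a month of any length.

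If the true day is uniform over a 30-day month, the share falling after the ECOD is (30 - d)/30: 22/30 = 73% for d = 8, 15/30 = 50% for d = 15, and 5/30 = 17% for d = 25. The rule counts all of these.

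**2. Conflicts within that month.**
- ECOD 8 September, patient seen alive on 20 September, death later in September with the day unknown: dated 5 September and counted.
- ECOD 30 September, patient dies on 6 September, non-fatal event in September with the day unknown: dated 16 September, after the death.

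**3. Year-only death, last contact alive in an earlier year.**
- Last contact alive 1 October 2018, death in 2019, later ECOD. Lower bound 1 January 2019, upper bound 1 October 2018. They are 92 days apart, so the mean is 1 October + 46 days = 16 November 2018.
- ECOD 8 September 2018, last contact alive 1 March 2018, death in 2019. The bounds are 306 days apart, so the mean is 1 March + 153 days = 1 August 2018. A death after the ECOD is moved inside the primary scope.
- Taking every possible last-contact day in 2017 with a death in 2018 and a later ECOD, 364 of 365 days give a death date in 2017. Only 31 December 2017 gives 1 January 2018.

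**4. Size of rule 1.** The control rate is 7.5% per year (SAP 4.6). With HR 0.80 the other arm has 6.0%, an average of 6.75%, rounded here to 7%.
- All 6,500 patients at risk: 6,500 x 0.07/12 = about 38 events per month.
- Allowing for 1,015 patients with events and about 240 who have left (6,500 x 1.5% x 2.5 years), about 5,250 remain: 5,250 x 0.07/12 = 30.6, or about 30.
- If 1-5% lack a day (an assumption): 0.01 x 30 = 0.3, up to 0.05 x 38 = 1.9 events under the rule.
- Wrongly included: at d = 8, 73% of these, about 0.2-1.4; at d = 15, about 0.15-0.95; at d = 25, about 0.05-0.3.

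**5. Effect on power.** With power = Phi(sqrt(D) x |ln HR|/2 - 1.96) and an assumed diluted HR of about 0.816, D = 1,015 gives 90.1%, D = 1,025 gives 90.3% and D = 1,005 gives 89.8%. Ten events either way move power by about 0.3 points.

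**The case against.** Several points on the other side stand.

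- **Rule 1 is often sensible.** Its output lies in the known month and is a fair midpoint whenever the event did precede the ECOD. A reader might infer that every date it returns is wrong or impossible. The text does not support that: impossible dates need an unknown day, the ECOD month, and a death or a last contact in that same month.
- **Part 2 depends on a definition.** Appendix A builds last contact alive from contacts with the patient or a third party and lists a vital status date among its inputs. If the contact that reported the death counts, last contact alive falls in or after the year of death and the bounds need not cross. The text does not settle this. That reading has its own cost: a year-only death learned of in the year it occurred would be dated the day after it was reported. Appendix A's setting of last contact alive to the day before death needs an available death date, so it does not clearly help with a partial one.
- **Partial dates should be few.** Investigators' best-estimate dates are collected, primary events are adjudicated, and a vital-status call follows one month after EOT.
- **A check is already planned.** The overall-study-duration sensitivity analysis has no ECOD cap, so being inside or outside does not matter there.
- **A midpoint rule is also all-or-nothing.** For d = 8, the midpoint of the whole month excludes every such event, wrongly for 8/30 = 27%. That is still fewer than the 73% wrongly included now. For an ECOD on or after about day 16 it includes them all, as the SAP does.

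**Conclusion.** Both bounding errors are present in the text as written. Rule 1 always returns a date on or before the ECOD and lacks bounds at death and last contact. The year-only rule gives crossed bounds for a death in a year after last contact alive, conditional on how Appendix A treats the contact reporting the death. Both depart from Protocol 10.3.3.5, and the first also cuts across the exclusion of post-ECOD events from the primary analysis.

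The consequence is minor. About 0.3-2 events fall under rule 1, and only the post-ECOD share of those is misclassified. This rests on the assumed 1-5% of missing days, a uniform event day and a monthly count of 30-38. For part 2 no frequency can be derived from the documents.

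A reader might infer that the rules favour rivaroxaban or put the primary conclusion at risk. Neither follows: the rules take no account of treatment, and even a shift of ten events would barely move power. This is a low-priority correction to prespecified derivation rules.

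**What to change.** First, state in Appendix A that, for imputing a death date, last contact alive is the last date on which the patient was known to be alive, and that it excludes the contact reporting the death. Without this, the lower bound below could itself pass the upper bound.

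Then replace both branches of SAP 4.3 by one rule:
- Lower bound: the latest of randomization + 1 day, the first day of the known period and, for a death, last contact alive + 1 day.
- Upper bound: the earliest of the last day of the known period, the date the event was reported and, for a non-fatal event, the date of death.
- Impute the midpoint, and only then compare it with the ECOD. Use neither the ECOD nor last contact alive as an upper bound for a death.

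If the report date does not bind, the examples become:
- Death after the 20 September visit: midpoint of 21 and 30 September, 26 September after rounding up, excluded with an ECOD of 8 September.
- Non-fatal event before the 6 September death: midpoint of 1 and 6 September, 4 September after rounding up.
- Either year-only death in 2019: 2 July 2019.

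The cost is a few lines of SAP text and derivation code before database lock.
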